Once received, the participants will be instructed to review the informed consent, and to ask any questions about the study to the Research Coordinator. If they are still interested in participating in the study, the potential participant will be given written instructions to indicate their choice on whether to opt in or opt out of audio recording by checking the desired box and adding their initials besides it, and to print, sign and date on the lines of the participant of the informed consent. Once this is completed, the participant will return the informed consent to the Research Coordinator. The signed document can be returned to the research team by: 1) mailing it in by USPS in a stamped envelope, 2) scanning or capturing an image the document and emailing it to the Research Coordinator, or 3) faxing it to the Research Coordinator.

Once the Research Coordinator receives a copy of the signed consent, the Research Coordinator will review the consent form to make sure everything is correct. Then, the Research Coordinator will sign and date the consent form under the lines for person obtaining

consent. Finally, the Research Coordinator will send a completed copy back to the patient for their records.

Once the informed consent is completed with both sets of signatures and the decision regarding audio recording, the research coordinator will send the participant their pre-appointment survey(s) (QBASE only for control patients, NEST and QBASE for intervention patients).

Due to the presence of COVID-19 currently in Ohio, but loosened guidelines we will re-instate recruitment procedures at CCF for NEST and control groups using electronic consent and offering audio to patients once again. We will limit our recruitment efforts to electronic outreach and consent only and will have patients fill out the survey electronically, as designated in the original protocol. We will go to the study site in person if the patient has opted for audio-recording or if the patient needs the NEST survey given to them.

B. MetroHealth

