We will utilize the same approach used at Cleveland Clinic to recruit pregnant women at the MetroHealth (MH) System with a few exceptions. These procedures have been discussed and agreed upon in conjunction with [name] who is a co-investigator as listed on the initial NIH application and the former site PI at MetroHealth and will be maintained by the new site PI, [name]. The language of the initial MyChart message will be slightly different, as the MetroHealth team believed this rewording could improve patient recruitment. Another key difference is that MH's system uses a call center but also PRS's, OB nurses, and selected research team members to scheduled patients. These parties will be given the MH specific phone script to inform patients about the study at the time of scheduling. If the patient would like further information on the study after scheduling, the scheduler will pass the patient information through to the MH study coordinator. These procedures have been discussed and agreed upon in conjunction with [name], co-investigator as listed on the initial NIH application and the former site PI at MetroHealth and will be maintained by the new site PI, [name].

Informed consent procedures for pregnant participants: All participants will be asked to provide their written informed consent prior to participation in the study. Informed consent will be obtained using an IRB-approved consent document by a trained research team member and obtained prior to data collection procedures. For pregnant patients and partners, this will take place prior to the scheduled clinical visit.

The original informed consent included authorization for both components of the study: survey completion and audio-recording the discussion during the prenatal visit about prenatal testing. In an effort to include participants who may want to complete the surveys but not have audio-recording, we have modified the informed consent document to designate participation in the survey component of the study with or without audio-recording (Created during the IRB renewal in June/July of 2018).

Electronic Email Consenting:

This method of enrollment will only occur if and when a participant cannot arrive early to their first OB appointment, or, if there is a time overlap in recruitment.

Informed consent will be obtained prior to data collection for this phase of the NEST study. Written informed consent will be obtained prior to data collection. The Research Coordinator will

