Due to the present of COVID-19 currently in Ohio, but loosened research restrictions, our MetroHealth team will now enroll NEST and Control patients either electronically or in-person (due to limited patient availability with electronic consent). MH patients will also be given the option of audio-recording. The MH research coordinator will present before the appointment if the patient is consented in person or needs the audio-recorder. If the patient enrolls electronically and does not wish to do audio, the MH research coordinator will send all forms electronically. If the patient does complete the forms electronically and does NOT consent to audio, the research coordinator will not present to the appointment to limit personal contact. The research coordinator will scan the completed NEST survey into the patient's chart on EPIC via Onbase. The coordinator will send an in-basket message to the provider saying that the survey was scanned in, and the coordinator will receive confirmation that the provider has received it.

If the first prenatal visit, for whatever reason, becomes a virtual visit, it will be documented and the following changes will be applied:

- Direct observation by means of audio recording will not be conducted. Therefore, the virtual visit will not be recorded in any way for the purpose of this study.
- Once the patient has sent the MH team her signed consent form electronically, they will send her the fully signed consent and links to the REDCap surveys 'NEST' and 'QBASE' with instructions to complete the NEST survey first (if applicable based on group).
- The research coordinator will scan the completed NEST survey into the patient's chart on EPIC via Onbase. It will be located in media manager and be linked to their appointment so the provider can view it before the appointment time. The coordinator will send an in-basket message to the provider saying that the survey was scanned in, and the coordinator will receive confirmation that the provider has received it his or her responding on there.

- The MH research coordinator will also send the completed NEST survey to the patient via email with instructions to use it during the discussion of prenatal genetics during their virtual visit.

II. Partners of pregnant patients enrolled in the study

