The research coordinator will obtain the providers' written informed consent for the study participation; a fully signed copy will be provided to the provider and another copy will be kept on file in a locked cabinet in [name] office at MetroHealth.

Following recruitment and informed consent procedures, OB providers will be randomized by practice into one of two study arms: (1) the intervention arm utilizing NEST or (2) the control arm utilizing standard practice patterns for education and counseling (usual care). Randomization by practice will prevent contamination between study arms, as a patient may see more than one provider within a practice over the course of her pregnancy. A cluster will be an outpatient clinic and contain the providers who practice at that location. The intervention will be delivered to the cluster as a whole. Thus, all participating providers within a cluster will be randomized to the same arm. Practices within the healthcare system will be stratified by both practice and patient-population characteristics. A binary random number generator will be used to assign NEST or control status at the practice level. The assignment will be checked to ensure a balance with respect to the number of clusters and providers in each of the study arms. Imbalances will be corrected manually, and the resultant groupings will be checked to ensure that randomization has been preserved. Participating providers in practices randomized to the intervention arm will receive a training session to orient them to NEST prior to data collection activities. Because NEST is targeted to affect the patient-provider interaction, study participants will not be blinded to which group they have been allocated.

All participating providers at Cleveland Clinic and MetroHealth will be asked to review the most current clinical practice guidelines as developed by the American College of Obstetricians and Gynecologists (ACOG) and Society for Maternal Fetal Medicine (SMFM). These guidelines will be emailed to each provider once their first patient has expressed interest in participating.

We will return to previous methods of enrolling providers into the NEST study at both MH and CCF.

DATA COLLECTION INSTRUMENTS AND PROCEDURES

We will utilize the same data collection instruments at both the Cleveland Clinic and at MetroHealth.

I. Pregnant participants

Data collection instruments and intervention:

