As a follow-up measurement, the Cleveland Clinic study team will conduct semi-structured interviews (Amendment #14). In doing so, we will gain further understanding of the decision-making process for prenatal genetic tests in addition to gain further information regarding the usability, feasibility and acceptability of the NEST intervention. Participants will include women who meet the criteria for the NEST study, and are either: in the 3rd trimester of pregnancy or have delivered in the last 12-months. This population reflects women who have completed the prenatal genetic test decision-making process and can provide key insight into ways to improve the best support that process. We will contact participants who meet inclusion criteria regarding participation in in-depth telephone interviews via MyChart or email, whichever has been the approved method (by the participant) for contact as part of the NEST study. Before re-contacting is initiated, a research team member will review to determine if individuals meet inclusion criteria. This will include a review of 1) the medical record of eligible participants to determine if any obstetrical complication has occurred that would constitute exclusion and 2) the research documentation to determine if an eligible participant withdrew or was withdrawn from the NEST study. These individuals will not be re-contacted.

3) Direct observation: We will use a method of direct observation (DO) to measure shared decision-making, the primary outcome of the study. We will measure this by audio-recording the visit and then using (1) the OPTION scale, a validated scale of shared decision-making and (2) a content checklist to assess the content and discussion of the visit. See Data analysis below for further description.

We will audio record patient-provider discussions during the first prenatal visit of those patients who provide written informed consent to do so. The research assistant will give the recorder to the patient to record the content, interaction, and duration of dialogue pertaining to genetic risk and risk assessment. We have elected to audio record instead of video record in an attempt to minimize the Hawthorne effect and because of the sensitive nature of the physical exam that takes place during this visit. Patients are given the option

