For those patients/partners and providers who both opt-in to direct observations, the audio will be summed in accordance with the OPTIONS scale instructions, and the results for patients/partners and providers will first be analyzed separately as a function of intervention (NEST vs. control). The data from patients/partners and providers will be combined in a data set matching patient and provider responses. The difference between matched pairs will be computed for SDM broadly, and components of SDM as described by OPTIONS will be computed individually, sorted by type of intervention, and, with the t-test, checked to see whether, within study arms, the means of the differences are significantly different from zero.

DATA MANAGEMENT

All study information will be maintained in a secure fashion as delineated by the Cleveland Clinic IRB, either in a locked cabinet in the WHI or on a secure, encrypted research computer. We will use IRB-approved level of encryption on the computer. Only research personnel will have access to these files. In addition, all personal identifying information recorded per IRB and informed consent purposes will be kept in a separate location from data to be used for analysis purposes.

Confidentiality of patient information will be maintained at all times. The study will have Institutional Review Board approval prior to recruitment of any patients at participating clinical sites. All study investigators and research team members will document completion of Human Subjects Protection Training prior to initiating any study procedures. This requirement may be met by completing the NIH course, the CITI (Collaborative Institutional Training Initiative) program, or another course as required by the member institution.

Cleveland Clinic:

Masterlist: A master list will be maintained that will allow researchers to link participants with their ID numbers only for the following purposes:

- 1) Documentation and distribution of gift card/ research stipend in appreciation of subject's time and participation in the study.
- 2) To link pregnant participants' and clinicians' responses during the data analysis phase as needed. Any linkage will be de-identified after data analysis is complete.
- 3) To investigate any adverse events: A data safety and monitoring protocol has been put into place. If any adverse events are identified, then the master list will be used to link the participant with her personal identifying information for this purpose.

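### The primary outcome exists only for visits where recording was agreed to after practices were allocated, and the plan neither checks nor corrects for opt-in that differs by arm

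*Combined protocol and SAP*

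**What the plan says.** - **Outcome.** Under Data collection procedures, item 3 (Direct observation): "We will use a method of direct observation (DO) to measure shared decision-making, the primary outcome of the study". The recordings are scored with the OPTION scale.
- **Who is recorded.** The same item says: "We will audio record patient-provider discussions during the first prenatal visit of those patients who provide written informed consent to do so". The section on informed consent for pregnant participants explains that the form was changed to "designate participation in the survey component of the study with or without audio-recording". An enrolled patient can therefore have survey data and no primary outcome.
- **Allocation.** Under III. OB providers: "OB providers will be randomized by practice into one of two study arms". The same paragraph says that "study participants will not be blinded to which group they have been allocated", and that NEST providers are trained before data collection.
- **Order of events.** A patient is eligible because she is booked with an enrolled provider, so her practice fixes her arm. On the email consent route, at both health systems, the audio choice is marked on the signed form. The coordinator then sends QBASE alone to control patients, or NEST and QBASE to intervention patients. The coordinator must know the arm to do this.
- **Virtual visits.** Under B. MetroHealth, if the first visit becomes virtual: "Direct observation by means of audio recording will not be conducted".
- **Analysis.** The Data Analysis section summarises the audio "For those patients/partners and providers who both opt-in to direct observations" and compares NEST with control. It also plans a multivariable analysis with baseline knowledge and attitudes, partner presence and provider characteristics, keeping variables that pass collinearity checks. It does not mention opt-in rates, unrecorded patients, missing outcomes or sensitivity analyses.

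**The concern.** In a cluster trial, randomisation balances the practices. It does not balance a subset of patients who enter the analysis through a voluntary choice made after allocation, when that choice is sought by staff who know the arm. If patients who agree to be recorded are those who would engage more (or less) in shared decision-making, and the strength of that selection differs between arms, the arms differ in OPTION score even if NEST does nothing. The same mechanism can hide a real effect. As the plan stands, a reader of the results could not separate an effect of NEST from a difference in who was recorded.

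**Working it through.** **What can be reproduced.** For the main trial the documents give no sample size, power, alpha, outcome SD, number of practices or expected opt-in rate. The target of 40 belongs to the interview sub-study. There is no planned figure to reproduce, so the size below is an illustration on assumed inputs.

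**Model (assumed).** No true NEST effect. OPTION score with SD 1. A patient opts in when a standard normal willingness variable, correlated ρ with her score, exceeds the threshold that gives opt-in proportion p. The mean score among those recorded is then ρ·φ(z)/p, where z is the normal quantile for p and φ is the normal density. The bias in NEST minus control is

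ρ × [φ(z_N)/p_N − φ(z_C)/p_C].

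**Selection terms.**
- p = 0.7: 0.3477/0.7 = 0.497
- p = 0.5: 0.3989/0.5 = 0.798
- p = 0.8: 0.2800/0.8 = 0.350
- p = 0.4: 0.3863/0.4 = 0.966

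**Same ρ in both arms.**

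| Opt-in, NEST vs control | Difference in terms | Bias, ρ = 0.2 | Bias, ρ = 0.5 |
|---|---|---|---|
| 70% vs 50% | 0.497 − 0.798 = −0.301 | −0.06 SD | −0.15 SD |
| 80% vs 40% | 0.350 − 0.966 = −0.616 | −0.12 SD | −0.31 SD |
| 50% vs 70% | 0.798 − 0.497 = +0.301 | +0.06 SD | +0.15 SD |

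With positive ρ, the arm with the higher opt-in is less selected and so looks worse. Higher opt-in under NEST would mask a benefit. Higher opt-in under control would create one.

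**Equal rates, different selection.** At 50% in both arms, with ρ = 0 in control and 0.3 in NEST, the bias is 0.3 × 0.798 − 0 = +0.24 SD. With equal rates and equal ρ it is zero. Similar opt-in rates are therefore not enough to dismiss the problem.

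**Effect on a test.** Take ρ = 0.3 and 70% vs 50%: the bias is 0.3 × (−0.301) = −0.09 SD. With an assumed 100 recorded visits per arm and clustering ignored, the standard error is √(2/100) = 0.141 SD, so the test statistic shifts by 0.09/0.141 = 0.64. A two-sided 5% test then rejects with probability 1 − Φ(1.96 − 0.64) + Φ(−1.96 − 0.64) ≈ 9.8%. Clustering would widen the standard error and lessen this inflation, but it would leave the bias in the estimate unchanged.

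**The case against.** Recording needs consent, so some opt-in is unavoidable. The planned multivariable analysis also includes baseline knowledge and attitudes, which should capture part of patient engagement. Both points are fair. However, the model is fitted to recorded visits only, its covariates are chosen for collinearity and not because they predict opt-in, and nothing in the plan would show whether recorded and unrecorded patients differ.

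A reader might infer four stronger claims, which the documents do not support:

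- **That staff presence at the visit depends on arm, so the opportunity to record does too.** The COVID-era Cleveland Clinic text says staff attend "in person if the patient has opted for audio-recording or if the patient needs the NEST survey given to them". Attendance there follows an audio choice already made on the consent form, and any patient in either arm who chose audio gets a staff visit. NEST can also be completed online, and the MetroHealth attendance rule does not mention arm. Differential opportunity is not shown.
- **That the patient knows her arm when she chooses.** Participants are unblinded, but no timing is given. On the email route, arm-specific surveys come after the choice. What is documented is that the study team knows the arm. The documents do not time the provider's own agreement to recording, and provider consent precedes randomisation, so the point rests mainly on the patient's choice.
- **That virtual visits are never recorded.** That rule is stated only for MetroHealth and covers both arms. It removes outcomes but is not evidence of differential loss.
- **That the bias would favour NEST.** Its direction depends on which arm has the higher opt-in and on how selection works in each.

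**Conclusion.** The concern holds as a risk of selection bias that the plan leaves unexamined. The three facts that create it are documented: the outcome needs a recording, recording is a choice made after allocation and sought by staff who know the arm, and the comparison is made in recorded visits without a check on that choice. The sizes shown, from a few hundredths to about 0.3 SD in either direction, rest entirely on assumed opt-in rates, an assumed correlation and a normal selection model. A 40-point gap in opt-in has no support in the documents and marks the far end of the illustration. The documents do not show that bias occurred. The change should be made before the arms are compared, because it is cheap and the data it needs are already being collected.

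**What to change.** 1. **Consent order.** On every consent route, use the same script in both arms and record the signed audio choice before any arm-specific material is given. The email route already has this order for the surveys; state it for in-person consent too.
2. **Reporting and sensitivity analysis.** Report opt-in by arm and by practice, and compare recorded with unrecorded patients on QBASE within each arm. Prespecify a sensitivity analysis of the between-arm OPTION comparison that allows for clustering by practice and uses inverse-probability-of-recording weights, estimated within arm from QBASE variables, health system and calendar period. The Data Analysis section does not specify a clustered model, so this one must be written out. At MetroHealth, restrict the target population to in-person visits: virtual visits there have no chance of being recorded, and no weight can recover them.
3. **Cross-check.** The measures table schedules shared decision-making items at QPV, which need no recording. Use them as supportive evidence only: they are unblinded self-report, have their own non-response and measure a different construct from observer-scored OPTION.
4. **Conclusion rule.** If weighted and unweighted results disagree, report the result as a difference among recorded visits and not as the effect of NEST in enrolled patients.

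The cost is script wording, some tables and one extra analysis, with a small loss of precision in the weighted estimate. The weights correct only for selection explained by the measured variables, and the report should say so.

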Data collection procedures:

1) QBASE: Once informed consent has been obtained, participants will complete the QBASE. This will be administered on a CCF-compliant tablet and using REDCap survey. Partners will complete their own survey independent from the pregnant participant.

2) Direct observation: Partners will be included in the DO as they will be present for the visit (see above for details).

3) QPV: This survey will be administered approximately 7-10 days following the first visit when the basic concepts associated with prenatal genetic testing have been introduced. It will be administered using online using REDCap survey. Unless otherwise specified by the participant.

All partners will receive a research stipend of the following amounts for each of the completed surveys from the Cleveland Clinic Accounts Payable Offices (partners will receive up to \$50.00):

- 1) QBASE - \$25.00
- 2) QPV - \$25.00

Of note, partner-participants will complete each of these instruments separate from the pregnant-participant. Responses will not be shared among a patient-partner pair.

Due to the presence of COVID-19 in Ohio, we will temporarily suspend recruitment of partners.

III. OB providers

We will utilize the same data collection instruments and procedures at both the Cleveland Clinic and MetroHealth.

Data collection instrument:

OB providers will complete a baseline questionnaire, OBP, at the time of enrollment. This survey will collect the following information: (1) prenatal appointment discussion points, (2) provider familiarity, (3) provider confidence in prenatal testing topics, (4) opinions on advancing prenatal genetic tests, (5) shared decision-making, and (6) decision-making preferences.

Data collection procedures:

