Data from the surveys will be collected either 1) using a tablet PC enabled with REDCap Survey for direct data entry or, if necessary, due to technical issues 2) on paper surveys with manual entry by the research team into REDCap. This is only done if there is a technical issue with the iPads or printers (internet connectivity problems, battery issues, etc.).

The following analysis will be conducted with the Principal Investigator in conjunction with [name], the QHS statistician designated to the WHI using JMP and SAS:

Data from the direct observation will be analyzed using the *observed* OPTIONS scale. This is a validated scale similar to the *dyadic* OPTIONS scale but developed for direct observation measurement of SDM in the clinical encounter. The *observed* OPTIONS scale will be utilized in conjunction with a content checklist to determine if the information exchanged during discussions of prenatal genetic risk and assessment meets the needs and preferences of patients, the recommendations of OB providers and GCs published by the American College of Obstetricians and Gynecologists, and clinical practice guidelines. The checklist was developed using data from our preliminary studies.

Audio recordings from the direct observation will be transcribed verbatim for analysis. Transcriptions will be coded by two independent coders using the *observed* OPTIONS scale and content checklist. Measures will be analyzed as a function of exposure (NEST vs. control) and visit composition (patient only vs. patient/partner pairs). The content checklist will be utilized to assess discussion content and to determine fidelity to the intervention. Transcriptions will be time-stamped to determine the length of discussions pertaining to prenatal genetic risk and assessment in NEST vs. control groups. Tukey-Kramer comparisons will be made to adjust for multiple comparisons. The matrix of predictor variables of intervention, patient characteristics, including variables of baseline knowledge and attitudes, presence of partner at the visit, and provider characteristics will be examined using the co-linearity tests of variance inflation factors and condition indices. Those variables exhibiting sufficient independence will be included in the multivariable analysis. Kappa statistics will be calculated to assess the degree of agreement between the coders; a third coder will be brought in if consensus cannot be reached.

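### The matched patient–provider SDM analysis tests each arm against zero, states no NEST-versus-control contrast of the difference, and has no documented visit-level scores to subtract

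*Combined protocol and SAP*

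**What the plan says.** Shared decision-making (SDM) measured by direct observation is the primary outcome (Study Design, Methods; Direct observation under the pregnant-participant procedures). The Data Analysis section treats it in two places.

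- **Direct-observation measures.** The instrument is the observed version of OPTION, described as "developed for direct observation measurement of SDM in the clinical encounter". Two coders, working separately, rate each transcript with it and with a content checklist. An arm comparison is planned: "Measures will be analyzed as a function of exposure (NEST vs. control"), followed by a multivariable analysis with intervention among the predictors.
- **Matched pairs (last paragraph of the section).** The audio is summed by the OPTIONS instructions, and "the results for patients/partners and providers will first be analyzed separately as a function of intervention (NEST vs. control"). The next step is a linkage: "The data from patients/partners and providers will be combined in a data set matching patient and provider responses". A within-pair difference is then taken, once for SDM as a whole and once for each OPTIONS component. These differences are grouped by arm and, by t-test, "checked to see whether, within study arms, the means of the differences are significantly different from zero".

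On the provider side, "OB providers will complete a baseline questionnaire, OBP, at the time of enrollment". It contains general SDM items. The only later provider survey, OBP-F, goes to NEST providers alone and asks whether they are using the tool.

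**The concern.** The study hypothesis is comparative: NEST should improve the SDM process relative to usual care. A test of whether the mean patient–provider difference is zero within one arm answers another question, namely whether the two parties systematically disagree in that arm. Two such tests, one per arm, do not estimate or test how far NEST changed the disagreement. A reader who sees significance in one arm and not in the other could easily take that for an effect of NEST.

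The subtraction also needs two scores for each visit, one from the patient side and one from the provider side, overall and by OPTION component. If the protocol does not say where they come from, the analyst must either improvise with instruments that do not match or leave the analysis out. Finally, a plain t-test treats pairs as independent, although several patients may share a provider and whole practices are randomised.

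**Working it through.** **1. What is tested.** The matched-pair step tests mean difference = 0 in NEST and, separately, mean difference = 0 in control. The quantity that bears on the hypothesis is (mean difference in NEST) − (mean difference in control). No test or interval for it is stated. The arm comparisons in the same section concern the direct-observation measures and the patient/partner and provider results taken separately, not the paired difference.

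**2. Where the two scores could come from.**
- *OPTION from the audio:* rated by two coders from the transcript of the visit. Neither the patient nor the provider rates it, and no split into a patient score and a provider score is described.
- *Dyadic OPTION:* mentioned only as a similar scale; no administration is described.
- *Patient surveys:* the measures table marks SDM items at QBASE, QPV, QTT and QFF, but they are not described as OPTION.
- *Provider OBP:* has SDM items, not described as OPTION, and is completed once at enrolment, so it cannot describe a particular visit. If it were used, the same fixed provider value would be subtracted for every patient of that provider.
- *OBP-F:* NEST arm only and about use of the tool.

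So no visit-level patient-rated and provider-rated pair is documented. The separate patient/partner and provider results at the start of the same paragraph have the same gap.

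**3. Size if an arm effect were read from the two within-arm tests.** The documents give no main-trial sample size, power or alpha, so there is no stated figure to reproduce. Assumptions: the arms are independent, the true difference is the same in both, and each test rejects with probability p. Then P(exactly one significant) = p(1−p) + (1−p)p = 2p(1−p).
- p = 0.05 (true difference zero, two-sided 5% test): 2 × 0.05 × 0.95 = 0.095
- p = 0.2 or 0.8: 2 × 0.2 × 0.8 = 0.32
- p = 0.5: 2 × 0.5 × 0.5 = 0.50, the maximum
- p = 0.9: 2 × 0.9 × 0.1 = 0.18

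A simulation agrees. It used 20,000 trials per setting, 25, 50 or 100 independent pairs per arm, and a standardised mean difference of 0 to 0.4, equal in both arms. The within-arm tests disagreed in 4.6% to 50.6% of trials. A direct two-sample test of the same differences rejected in 4.6% to 5.2%.

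**4. Clustering.** The t-test names no adjustment. With m pairs per cluster and intracluster correlation ICC, both assumed, the design effect is 1 + (m−1) × ICC, and the actual two-sided error of a nominal 5% test is about 2[1 − Φ(1.96/√design effect)].
- m = 5, ICC = 0.01: design effect 1.04, error about 0.055
- m = 10, ICC = 0.05: design effect 1.45, error about 0.10
- m = 20, ICC = 0.10: design effect 2.90, error about 0.25

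**The case against.** The strongest reply is that the SDM outcome does have planned arm comparisons and that the matched-pair step is supplementary. This stands. A reader might infer that SDM is never compared between NEST and control; the Data Analysis section contradicts that, both for the direct-observation measures and for the separate results that open the matched-pair paragraph.

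Second, a within-arm test of concordance is coherent as description, and nothing in the text says that a NEST effect will be claimed because one arm reaches significance and the other does not. This also stands. That inference is a risk left open, not a stated plan. It follows that the 2p(1−p) figures do not give this trial's error rate: 50% is the worst case, and the result is about 10% when each test rejects 5% of the time.

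Third, a reader might infer that the paired analysis is impossible. The documents do not support that. They print neither the OPTION scoring rules nor the survey forms, patients do answer SDM items after the visit, and the Masterlist provisions allow patient and clinician responses to be linked. What is shown is that the source of each side of the pair is unspecified. Permission to link does not supply a visit-level provider rating, and none is described.

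Last, clustering affects every analysis in this trial. That is true; it is noted here because this t-test would need correcting in any case, and it does not by itself raise the severity.

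**Conclusion.** The point holds for the matched-pair analysis only. As written, that analysis can describe patient–provider concordance within an arm but cannot show that NEST changed it. Its inputs are also undocumented, and its t-test ignores nesting within providers and practices.

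The discordance range (about 10% to 50% at the values of p from 0.05 to 0.8 shown) is conditional on an interpretation that the plan does not state and on rejection probabilities that the documents do not give. The error range of about 0.055 to 0.25 rests on assumed cluster sizes of 5 to 20 and ICCs of 0.01 to 0.10. The finding on the scores rests on the instruments and procedures as listed, not on the scale manual. Because separate arm comparisons of SDM are planned, this is a should-fix item and not a threat to the trial as a whole.

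**What to change.** - State that the observed OPTION score per encounter (total first, then items) is compared between NEST and control with one treatment contrast and a 95% confidence interval. The model must account for practice and provider, for example a mixed model with both levels. The documents contain no such model, so it has to be written.
- Keep the matched-pair analysis only if a visit-level SDM rating exists from both patient and provider. If so, name the instrument, rater and time point for each side, test the arm coefficient for the paired difference in the same type of model, and report within-arm means descriptively.
- If no such ratings exist, delete the subtraction and the within-arm t-tests.

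The cost is analysis wording. The downside is that the concordance analysis is lost if there is no visit-level provider rating. Adding one would mean new data collection, which could cover only visits still to come.
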